Trial design and methods:	The trial consists of two non-randomised intervention substudies with before and after comparison (outpatient and inpatient), with embedded qualitative substudies involving clinician interviews and (in the outpatient setting only) observed consultations and patient interviews. Clinicians will be recruited, consented and provided with training to use the MiADE system. The system will be switched on at a particular time point, and clinical records for patients seen before and after the system was switched on will be compared. The primary outcome will be the comparison of the number of diagnoses, medication and allergies entered in a structured way per	

	patient. A rapid ethnography-based approach will be used to observe a subset of patient consultations to find out how clinicians are using the system, and semi-structured interviews will be held with patients and clinicians to understand the effect of social, cultural and behavioural information on human experiences and practices.
Trial duration per participant:	5 months
Key Study milestones	Jul 2023: Clinician recruitment and consent
	Aug 2023: Training of clinicians, surveys and observed consultations without MiADE
	Sep 2023: MiADE switch on
	Oct 2023: Interviews, surveys and observed consultations with MiADE
	Nov 2023: Study end
	Dec 2023 – Jan 2024: Data analysis
Estimated total trial duration:	7 months
Planned trial sites:	Single-site, UCLH
Total number of	Outpatient study:
participants planned:	Clinicians using MiADE: at least 25, target 50
	Patients for analysis of pseudonymised health record: estimated 3000 (assuming 25 clinicians each see 5 new patients per week, and 24 weeks of data are analysed)
	Clinicians for observed consultations and interview: 5
	Patients for observed consultation and interview: at least 20 (10 before MiADE, 10 after MiADE)
	Inpatient study:
	Clinicians using MiADE: at least 25, target 50
	Patients for analysis of pseudonymised health record: estimated 600 (assuming 5 inpatient teams each discharge 5 patients per week, and 24 weeks of data are analysed)
Main inclusion/exclusion criteria:	Electronic health record of patients being seen in clinics under the care of participating clinicians
Statistical methodology	Outpatients: comparison (pre- and post-intervention) of mean

Feasibility study of 'MiADE' point of care natural language processing, EDGE number 157134, IRAS number 322887, Protocol, Version 1.1, DATE 24/07/2023

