4. TRIAL DESIGN

This study consists of two substudies (inpatient and outpatient studies), each of which is a nonrandomised intervention study with before and after comparison. The outpatient study also includes an embedded qualitative substudy for a subset of consultations, with patient and clinician interviews. A subset of clinicians will also be interviewed for the inpatient study. The overall clinician participant flow is illustrated in Figure 2.

[figure not shown]

Figure 2: Study flow diagram showing how clinicians will move through the study

Three time periods will be analysed. The primary comparison will be for recording of structured information in patient records between pre-MiADE and post-MiADE periods once clinicians have been consented into the study, as they will have received training and the comparison will show the change in behaviour that results from the system being available. There is a possibility that structured recording may improve because of the study itself (i.e. a Hawthorne effect), so a prior 8week period will also be studied in order to evaluate this effect. See figure below for the overall trial design and timing of interventions. The overall study timeline is shown in Figure 3.

The MiADE system will be made available according to clinician-level permissions, which can be switched on or off. This will allow clinicians' use of problem lists and other structured data to be compared before and after the system is switched on. There will be a period of at least 4 weeks between clinicians entering the study and having the MiADE system switched on.

[figure not shown]

Figure 3: Study timeline

Training programme

All clinicians in the study will undergo a standardised training package consisting of viewing a video and reading a user guide, with access to help from the research team by email or phone throughout the study. The training will cover:

- The importance of maintaining problem lists with accurately coded information about a patient's diagnoses
- National and local (UCLH) guidance on the use of problem lists
- How to use the MiADE system
- The aims and methods of the study

Clinicians will not be eligible to enter the study and have the MiADE system switched on for their EHR user profile until they have undertaken the training.

Pre-MiADE questionnaire – questions for all clinicians

- What is your seniority (e.g. FY1, Consultant etc.)?
- What is your specialty?

Pre-MiADE questionnaire – outpatient study

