Inpatient clinical teams will be recruited to the study. Within each team, the clinicians (consultants, specialty and foundation doctors who see inpatients) will be recruited, consented and trained. Doctors rotate through clinical teams every few months, so the MiADE system will be switched on for the relevant clinicians at a time point half-way through the four-month rotation, to allow comparison of the completeness of structured recording of diagnoses on the problem list before and after the switch-on. The 'gold standard' of recording of diagnoses will be the ICD-10 coded billing diagnoses which are assigned by the clinical coding team based on a review of the entire medical record after a patient is discharged. Diagnoses will be aggregated by groups of ICD-10 codes similar to a previous UCLH audit [15], and a diagnosis will be considered as included in the problem list if any SNOMED CT concept which maps to an ICD-10 code in the group was recorded on or prior to the patient's discharge date. This flexibility of mapping will be permitted as different professionals may assign different clinical codes to the same condition based on their interpretation and judgement, especially for cases where an exact code does not exist. The proportion of ICD-10 code groups with a problem list entry will be calculated per patient, and aggregated across the patients under the care of the clinical team during the study period.

For a sample of 5 clinicians, semi-structured interviews will be held with the clinicians after they have been using MiADE for at least two weeks, using the same questions as for outpatient doctors except the question on medications, as MiADE for inpatients does not handle medications.

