10.6.4 Sensitivity and other planned analyses

Subgroup analyses for the completeness of structured data recording will be carried out by clinical specialty and seniority of doctor. Correlations between clinician characteristics in the pre-MiADE survey and the difference in mean number of structured entries with MiADE for outpatients will be explored.

Secondary analyses will be carried out to compare recording of structured data between the following time periods:

- 1. Before consent versus before MiADE. This will assess the Hawthorne effect, i.e. if there is any change in clinician behaviour once they know they are in the study. This will provide useful information for future interventions to improve structured data recording.
- 2. Before consent versus after MiADE. This will assess the overall effect of the complex intervention (i.e. the whole programme of training, institutional buy-in for quality improvement, as well as the tool to assist clinicians).

There are no relevant stopping criteria.

11.ASSESSMENT AND MANAGEMENT OF RISK

The table below summarises the risks and mitigations of all interventions above standard care that are being performed:

Intervention	Potential risk	Risk Management
Entering clinical data using MiADE	MiADE may return an inaccurate suggestion (possible)	The clinician has to actively review a suggestion in order to add it to the record, so there is minimal risk that an incorrect entry will be added to the patient record.
Entering clinical data using MiADE	Clinicians may not use the system appropriately (possible)	Training will be provided and access will be limited to clinicians who have completed training.
Entering clinical data	The MiADE system may malfunction	The MiADE system is separate from Epic and works in the

using MiADE	(unlikely)	background, so users can continue with their Epic work regardless of the activity of MiADE. If Epic does not receive a reply from MiADE in a reasonable time it will timeout the request. If the MiADE system is completely down, clinicians will be able to use Epic just as before, without MiADE.
Entering clinical data using MiADE	The MiADE system may perform poorly and be a hindrance to clinicians (unlikely)	Clinicians can choose to ignore the recommendations from MiADE or switch the system off at any time.

12.RECORDING AND REPORTING OF ADVERSE EVENTS

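### In Study 2 the pre-consent window reaches into the previous rotation, so the planned Hawthorne and whole-programme comparisons cross a change of rotating doctors

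*Protocol*

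**What the plan says.** Protocol section 4 (Study 2) notes that "Doctors rotate through clinical teams every few months" and for that reason plans that "the MiADE system will be switched on for the relevant clinicians at a time point half-way through the four-month rotation". Within each team, "the clinicians (consultants, specialty and foundation doctors who see inpatients) will be recruited, consented and trained".

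The general part of section 4, which introduces both substudies, says "Three time periods will be analysed". The primary comparison is between the post-consent period without MiADE and the period with it. To look for a Hawthorne effect, "a prior 8week period will also be studied in order to evaluate this effect". On spacing: "There will be a period of at least 4 weeks between clinicians entering the study and having the MiADE system switched on". No upper limit is given.

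The Study Summary sizes the inpatient extract by "assuming 5 inpatient teams each discharge 5 patients per week, and 24 weeks of data are analysed". Section 7.7 ends the trial 8 weeks after the last switch-on.

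Section 10.6.4 plans two secondary comparisons that use the pre-consent window. Comparison 1, "Before consent versus before MiADE", is read as showing whether clinicians behave differently once they know they are being studied. Comparison 2, pre-consent against post-MiADE, is read as the effect of the whole programme. Neither is restricted to Study 1. Section 10.6.2 adds that inpatient results cannot be attributed to individual clinicians within a team.

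**The concern.** Switching on mid-rotation protects the primary contrast from doctor turnover, but the pre-consent window has no such protection. If that window starts before the rotation does, part or all of it was recorded by rotating doctors who had left the team before the study period. Comparison 1 then sets one group of doctors against another, and a difference between the groups would be reported as a reaction to being studied. Comparison 2 has the same mixture, although its stated target is the programme and not individual behaviour. Section 10.6.4 says comparison 1 should inform future interventions, so a misreading would carry forward.

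**Working it through.** **Plan's own figure.** Inpatient records: 5 teams × 5 discharges per week × 24 weeks = 600, as the Study Summary states. The inpatient extract is therefore planned to span 24 weeks.

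**Inputs**
- Rotation length R: four months (section 4, Study 2) = 4 × 52/12 = 17.33 weeks.
- Switch-on: R/2 = week 8.67 of the rotation.
- Interval from consent to switch-on, L: at least 4 weeks (section 4).
- Pre-consent window: 8 weeks (section 4).
- Post-MiADE period: 8 weeks (section 7.7).

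**Does 24 weeks fit in one rotation?** No: 24 − 17.33 = 6.67 weeks must fall outside it, however the span is divided. If the last 8 weeks follow switch-on, the data end at week 8.67 + 8 = 16.67 and start at 16.67 − 24 = −7.33, which is 7.33 weeks before the rotation begins.

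**Share of the pre-consent window in the previous rotation.** The window runs from week 8.67 − L − 8 to week 8.67 − L, so

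share = min(8, max(0, 8 + L − 8.67)) / 8.

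| L (weeks) | Consent at week | Window (weeks of rotation) | Share before rotation start |
|---|---|---|---|
| 4 (the minimum) | 4.67 | −3.33 to 4.67 | 3.33/8 = 42% |
| 6 | 2.67 | −5.33 to 2.67 | 5.33/8 = 67% |
| 8 (24 weeks as 8 + 8 + 8) | 0.67 | −7.33 to 0.67 | 7.33/8 = 92% |
| 8.67 or more | 0 or earlier | wholly before 0 | 100% |

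A zero share would need L ≤ 8.67 − 8 = 0.67 weeks, which the 4-week minimum rules out.

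**Sensitivity of the 42%.** With a rotation of 120 to 123 days the share at L = 4 is 43% to 40%. With a rotation read as 16 weeks it is 50%.

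**Primary contrast.** The post-MiADE period is weeks 8.67 to 16.67, with midpoint 12.67. The period between consent and switch-on has midpoint 8.67 − L/2.
- L = 4: weeks 4.67 to 8.67, midpoint 6.67, gap 6.0 weeks.
- L = 8: weeks 0.67 to 8.67, midpoint 4.67, gap 8.0 weeks.
- L = 8.67: weeks 0 to 8.67, midpoint 4.33, gap 8.33 weeks.

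Both periods lie inside one rotation, so the rotating doctors are the same, and the later period is always later in post. The two full halves of a rotation have midpoints 8.67 weeks apart. With a 4-week baseline, a linear trend over the rotation would therefore enter the primary difference at 6.0/8.67 = 69% of the half-to-half change, not in full.

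**The case against.** **Does the window apply to Study 2?** The three-period layout is explicit for outpatients. The Study 2 text describes only before and after switch-on, and section 5.1 takes inpatients managed during the study period. Applying the pre-consent window to inpatients rests on the general text of section 4, the unrestricted wording of section 10.6.4 and the 24 weeks in the Study Summary. Together these make it the natural reading, but the 8 + 8 + 8 split behind the 92% is inferred.

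**Do the doctors really differ?** Only the rotating ones. Teams include consultants, who may stay, and the Protocol does not say which grades rotate or whether change dates coincide. This limits how much of the team changes. It does not rescue the comparison, because section 10.6.2 rules out separating results by clinician within a team.

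**Is comparison 2 misread?** Section 10.6.4 ties individual behaviour to comparison 1 only. Comparison 2 concerns the programme and can be read at team level. That stands, but turnover is still mixed into it.

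**The tempting stronger reading.** A reader might infer that the primary Study 2 result is itself invalid because settling into a post would pass for a MiADE effect. The Protocol does not support that. Mid-rotation switch-on is a reasoned choice that keeps the same doctors on both sides, and lack of a concurrent control is inherent in a declared single-arm before-and-after feasibility study. Nothing in the document gives the size or direction of any drift over a rotation, and with a 4-week baseline the earliest weeks in post are excluded. What remains is alignment with time in post, of unknown size.

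**Conclusion.** The point holds for the two secondary comparisons that use the pre-consent window in Study 2. On the Protocol's own timing rules, at least about 42% of that window precedes the current rotation. The share is about 92% if the 24 weeks are three equal periods and 100% if consent is at or before rotation start. Comparison 1 therefore cannot show a Hawthorne effect for inpatients, and comparison 2 confounds the programme effect with a change of rotating doctors.

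This assumes that the window applies to Study 2, that the rotation is four months as stated, and that at least some team doctors change at its start. The outpatient comparisons are not affected, nor are the planned numbers of records. The primary Study 2 contrast stands as designed, with time in post as a limitation to be acknowledged.

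**What to change.** In section 10.6.4:
1. Limit the Hawthorne interpretation of comparison 1 to Study 1.
2. For Study 2, describe comparisons 1 and 2 as team-level historical comparisons that cross a change of rotating doctors, and do not interpret them as changes within clinicians.

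With the primary Study 2 analysis, state that the contrast holds the rotating doctors constant but is aligned with their time in post, and that the size of any resulting bias is unknown.

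The cost is a few sentences. No new data are needed, and the primary analysis and sample size do not change.

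Optional, not required: extract the same teams' previous rotation, split it at its own midpoint, and report the difference between the two rotations' within-rotation changes as a supporting analysis. This needs about 17 weeks of earlier records instead of 8, and possibly a minor amendment because section 5.1 limits inpatients to the study period. It also assumes that different doctors share the same trend over a rotation. With similar numbers per period, its standard error is about √2 ≈ 1.4 times that of the primary difference.

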5. SAMPLING METHODS

Study 1 (outpatient): Clinicians who carry out outpatient clinics will be eligible to take part. Clinicians for the observation substudy will be purposively sampled from the interested clinicians to include a range of specialties and seniorities. One or more face to face clinics will be sampled before and after MiADE, and consecutive patients booked to attend the clinics will be invited to have their consultation observed as part of the study.

Study 2 (inpatient): Inpatient teams will be recruited to the study. All clinicians within interested teams will be eligible to be included. All patients managed by these teams will be included for pseudonymised analysis of their health records.

5.1 Inclusion criteria

Study 1 clinician inclusion criteria: Any interested clinicians who have their own clinic list at UCLH and see outpatients, who consent to be part of the study. A subset of at least 5 clinicians will be purposively sampled to include a range of specialties for the observation substudy, and they will undergo observed consultations.

Study 1 patient inclusion criteria: All outpatients seen by the clinician from 2 months before being consented until 2 months after the MiADE system is switched on for included clinicians. For clinicians selected for observation (at least 5), we will observe at least 2 consultations from one or more clinics before and 2 consultations from one or more clinics after the MiADE system is switched on will be observed. Hence the minimum number of observed consultations will be 20.

Feasibility study of 'MiADE' point of care natural language processing, EDGE number 157134, IRAS number 322887, Protocol, Version 1.1, DATE 24/07/2023

Study 2 clinician inclusion criteria: All clinicians within interested inpatient teams at UCLH.

Study 2 patient inclusion criteria: All inpatients managed under the care of a participating team during the study period.

5.2 Exclusion criteria

Patients who lack capacity to consent will not be eligible for inclusion in the observed consultations and patient interviews.

5.3 Recruitment

Clinicians will be recruited via clinical networks and clinical operational structures within the hospital such as Divisional meetings and the Epic Expert Community.

Consecutive patients from selected clinics will be recruited for the outpatient qualitative substudy.

Participant recruitment at a site will only commence when the trial has:

- Been confirmed by the Sponsor (or its delegated representative), and
- Been issued with Confirmation of Capacity and Capability from each participating site (where applicable).

5.4 Informed Consent

Clinician participants

Informed consent will be sought from all clinician participants. Consent will be sought from patients whose consultation is being observed as part of the qualitative substudy. For patients whose deidentified data are being used for analysis, an opt-out model will be used, in common with other studies using de-identified patient data at UCLH.

It is the responsibility of the Investigator, or a person delegated by the Investigator to obtain written informed consent from each participant prior to participation in the trial, following adequate explanation of the aims, methods, anticipated benefits and potential hazards of the trial.

The person taking consent will be suitably qualified and experienced, and will have been delegated this duty by the CI/ PI on the Staff Signature and Delegation of Tasks.

Patient participants

For patients whose pseudonymised data are included in the study to assess recording of structured data, consent will not be sought.

For patients included in the outpatient observation substudy, written consent will be sought. Information about the study will be provided by the researcher prior to the clinic, and if the patient agrees to participate they will be asked to give written consent prior to their consultation. Adequate time will be given for consideration by the participant before taking part. Patients who lack capacity will not be eligible to participate in the observed consultation. The researcher will explain that participants are under no obligation to enter the trial and that they can withdraw at any time during the trial, without having to give a reason and without prejudicing his/her further treatment. Data collected up to the point of withdrawal can only be used after withdrawal if the participant has consented for this, and this will be outlined in the consent form. Where a participant is required to re-consent or new information is required to be provided to a participant, the researcher will ensure that this is done in a timely manner.

No study procedures will be conducted prior to the participant giving consent by signing the Consent form.

A copy of the signed Informed Consent form will be given to the participant. The original signed form will be retained in the Investigator Site File and a copy placed in the medical notes.

The PIS and consent form will be reviewed and updated if necessary throughout the study and participants will be re-consented as appropriate.

5.4.1 Additional consent provisions for collection and use of participant data and human tissue in ancillary studies (if applicable)

Not applicable for this study.

6. **PRODUCT/INTERVENTIONS**

6.1 Name and description of intervention under investigation

The digital health technology being investigated in this study is MiADE, a natural language processing software system embedded within the electronic health record to facilitate the point of care recording of structured information in electronic health records. It is a Tier B technology according to the NICE evidence standards framework for digital technologies.

System overview

[figure not shown]
MiADE will interact with the 'Epic' electronic health record system via a user interface component called 'NoteReader'. NoteReader enables newly created text notes to be analysed by a third party NLP system, and presents structured data to the clinician for verification and entry into the record. NoteReader supports data entry for problem list entries (diagnoses), medication (including dosage), allergies and other custom data fields. The structured data entries suggested by the NLP system are displayed alongside the draft text note, and are discarded when the note is saved or 'committed' to the EHR. Thus the NLP suggestions do not form part of the medicolegal record, but exist temporarily only in the draft form of the document.

Epic NoteReader is already used by a number of US hospitals with third party commercial NLP systems, as well as one UK hospital (Great Ormond Street Hospital which is using 3M M*Modal Fluency as the third-party NLP system).

MiADE is an open source software system created by the research team which will be evaluated in this study. It is based on an information extraction and linking engine called MedCAT (Medical

Concept Annotation Tool) [16], with additional modules for dosage extraction, context detection, deduplication and integration with an EHR system.

Figure 4: Data flows between MiADE and Epic

